6.4 Sample Size and Power

The primary endpoint of this study is the difference between baseline MCC and MCC immediately after HS administration. In reviewing MCC data under baseline conditions in patients who would fit criteria for moderate asthma, Burbank *et al.* found a mean average % retention of 21% with a standard deviation of 9% (16). We wish to detect a difference of mean MCC equal to 7%. Given the paired nature of the study, we believe 10% to be a reasonable upper bound of the standard deviation of this difference in means. Assuming $\beta=0.9$ and $\alpha=0.05$, a sample size of $n=21$ would be adequate. We will inflate this by 30% to account for

attrition with multiple study visits, taking the recruited sample to n=28.

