2. STUDY OBJECTIVES

2.1 Primary Objective

This study will assess the efficacy of inhaled HS for accelerating MCC acutely in well-controlled moderate to severe asthmatics.

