6 STATISTICAL CONSIDERATION

6.1. Primary Endpoint:

change in MCC from baseline immediately after 7% HS inhalation

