6.2 Secondary Endpoints

a. change in MCC from baseline immediately after albuterol inhalation. This endpoint is of exploratory interest.

b. Safety measures for HS treatment in moderate to severe asthmatics will include change in the following from baseline:

- Vital signs (HR, RR, BP and oxygen saturation)
- Spirometry (FEV1, FVC)
- Symptom Questionnaires
- Physical exam (wheezing on chest auscultation, for example)

We will also assess:

- Adverse events and Serious Adverse events
- Proportion of participants who are deemed 'intolerant' to HS (i.e. those who experience a persistent reduction in FEV1 of $\geq 10\%$ from that day's baseline at 30 minutes post-HS, those who report shortness of breath, those who report a score of "3" for any individual symptom criterion, or those who experience oxygen saturation levels below 90% for > 1 hour).

Safety endpoints will be assessed continuously during the study period for monitoring of adverse events and individual stopping criteria. All adverse events whether or not listed in the NCI-CTCAE (see Section 9) or whether they are or are not related to study participation will be graded on a scale from 1 to 5 according to the standards in the NCI-CTCAE manual. Adverse events will be reported to the UNC IRB, the UNC DSMB, and the NHLBI project officer. The DSMB will review the protocol after 5 subjects have completed study procedures or at 6 months after enrollment begins, whichever is soonest, and then every 6 months thereafter.

Exploratory endpoints will also be assessed. These will focus on sputum cellularity, mediators in sputum (e.g. T1 cytokines: IL-1 β , IL-6, IL-8, TNF α , T2 cytokines, IL-4, IL-5, IL-13), eicosanoids,

and mucins (total mucins, MUC5AC, MUC5B).

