6.3 Statistical Methods

Our analytical plan was developed in collaboration with [name], the biostatistician for the CEMALB who will oversee all statistical analyses. The primary analysis of interest pertains to the difference between MCC measured at baseline and MCC measured during and after 7% HS challenge. The MCC measurements that define this difference are defined in section 5, and this difference has a unit of absolute percentage points. We will perform descriptive analysis of this difference; all point estimates will be tabulated along with their 95% confidence intervals. As we have assumed the sufficient underlying normality of MCC measurements, we will test the null hypothesis of no difference between baseline MCC and MCC immediately during and after 7% HS, against the alternative hypothesis of some difference, using a paired two-sided one-sample t-test with a 5% type I error rate. That is, if we let $\mu_{\Delta3\%}$ denote the mean difference between MCC measured at baseline and MCC measured during and immediately after the albuterol treatment, i.e. we will test the following hypothesis:

$$H_0: \mu_{\Delta\text{albuterol}}=0 \text{ vs. } H_1: \mu_{\Delta\text{albuterol}}\neq 0.$$

If the observed p-value is above 0.05, the test will be interpreted as being inconclusive. Following this test, we will perform sensitivity analyses to assess how realistic the assumption of normality was, and how much it may have impacted our conclusions. In particular, we will examine normal q-q plots and other descriptive tabulations, and we will examine the results of a Wilcoxon Signed Rank test. Should extreme or questionable observations arise in the study, we will also examine regression diagnostics to assess the influence of how those data were handled. The secondary analysis, which is of exploratory interest, pertains to the difference between MCC measured at baseline and MCC measured during and immediately after the 7% HS challenge. We will analyze this difference in a similar manner, i.e we will test the hypothesis

$$H_0: \mu_{\Delta7\%}=0 \text{ vs. } H_1: \mu_{\Delta7\%}\neq 0.$$

We will report the proportion of enrolled patients who do not tolerate HS at baseline, along with the 95% confidence interval of this proportion.

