The effect of albuterol treatment on MCC will be assessed as a secondary endpoint, using the same techniques as described above for studies of 7% HS. We will also compare results following treatment with albuterol to those observed after 7% saline as an exploratory outcome. To do this analysis, we will assess the difference of the outcomes of these treatments within each individual and conduct appropriate paired t-tests. If these differences are not normally distributed, we will do proper transformation of the data to achieve a normal distribution. We will also conduct Wilcoxon signed rank tests in when data are not normally distributed.

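### Section 6.3 displays the wrong hypothesis for the primary test; on the described visit steps the primary contrast is albuterol plus 7% HS but is worded as an HS effect, and the HS-visit versus albuterol-visit comparison has no single rank

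*Combined protocol and SAP*

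**What the plan says.** **The primary question.** Section 2.1 reads: "This study will assess the efficacy of inhaled HS for accelerating MCC acutely in well-controlled moderate to severe asthmatics". Section 6.1 gives the primary endpoint as "change in MCC from baseline immediately after 7% HS inhalation", and 6.4 sizes the study on the same contrast: "The primary endpoint of this study is the difference between baseline MCC and MCC immediately after HS administration". The synopsis primary objective is also worded as the efficacy of HS against baseline.

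**Section 6.3.** It opens in agreement: "The primary analysis of interest pertains to the difference between MCC measured at baseline and MCC measured during and after 7% HS challenge". The symbol then introduced for the test carries a 3% subscript and is said to "denote the mean difference between MCC measured at baseline and MCC measured during and immediately after the albuterol treatment". The displayed null is that the mean albuterol difference is zero. A later sentence begins "The secondary analysis, which is of exploratory interest, pertains to the difference between MCC measured at baseline and MCC measured during"; its remaining words show that the 7% HS scan is meant, and it has its own null.

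**The visits.** Sections 3.1 and 4.1 describe a Visit 1 scan with no albuterol step. Sections 3.1 and 4.3 describe 4 puffs of albuterol within the Visit 3 scan. Sections 3.1 and 4.5 describe 4 puffs of albuterol and then 4 mL of 7% HS within the Visit 5 scan. The HS inhalation text in section 5 says that everyone is pretreated with albuterol.

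**The comparison of the two treatment visits.** Section 6.2 lists only "change in MCC from baseline immediately after albuterol inhalation. This endpoint is of exploratory interest" as its MCC secondary endpoint. The end of 6.3 adds: "We will also compare results following treatment with albuterol to those observed after 7% saline as an exploratory outcome".

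**The concern.** Three things matter for how the result will be read.

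First, the hypothesis printed for the primary test is not that of the contrast named as primary. Anyone programming from the displayed hypotheses would test albuterol as primary and demote HS. Section 6.5 also plans interim efficacy analyses of 7% HS, so the hypothesis should be settled before any data are looked at.

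Second, if the baseline scan is albuterol-free, a significant Visit 5 minus Visit 1 result supports a statement about albuterol followed by 7% HS. Section 2.1 promises a statement about HS. The plan itself treats albuterol as a possible accelerator of MCC, since it gives it a separate scan visit.

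Third, the contrast that bears on what HS adds to albuterol has no settled status, and no precision is stated for it. A reader could not tell afterwards whether it had been planned as secondary or as exploratory.

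**Working it through.** **Step 1. Primary test, place by place.**

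| Place | Contrast treated as primary |
|---|---|
| Synopsis, efficacy evaluations and stated null | 7% HS visit vs baseline |
| Synopsis, primary endpoint sentence | mixes baseline, albuterol and 7% HS |
| 6.1, 6.4, opening of 6.3 | 7% HS visit vs baseline |
| 6.3, displayed hypothesis | albuterol vs baseline, 3% symbol |
| 6.3, later sentence | 7% HS vs baseline is secondary and exploratory |

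The final paragraph of 6.3 calls the albuterol effect secondary. The weight of the text favours 7% HS versus baseline as primary. Section 5.1 has a similar leftover, a comparison of 3% with 7% HS, although no visit gives 3% HS as a study treatment.

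**Step 2. What each contrast estimates.** Let b be the mean at an untreated scan, A the shift from albuterol, and H the further shift from 7% HS given after albuterol. Leave period effects aside. On the described steps the visit means are b (Visit 1), b + A (Visit 3) and b + A + H (Visit 5). Then:
- Visit 5 minus Visit 1 = A + H
- Visit 3 minus Visit 1 = A
- Visit 5 minus Visit 3 = H

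**Step 3. The condition.** Four places do not fit an albuterol-free Visit 1:
- the schedule in section 14 marks albuterol at Visit 1;
- 4.1 sets its FEV1 threshold as a value taken ahead of albuterol;
- the sputum induction text in section 5 measures FEV1 falls from a post-bronchodilator value;
- section 9 says 4 puffs were given 2 to 3 hours before induction.

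If albuterol did precede the Visit 1 scan, the Visit 1 mean would be near b + A. Visit 5 minus Visit 1 would then be close to H, and Visit 3 minus Visit 1 would no longer estimate A.

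**Step 4. Rank of Visit 5 minus Visit 3.** It is secondary in the synopsis objectives, the synopsis secondary endpoints and 2.2. It is absent from 6.2 and exploratory in 6.3. It can also be read into the synopsis primary endpoint.

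**Step 5. The plan's own sample size.** Inputs from 6.4: difference 7 points, SD 10 (given as an upper bound), two-sided alpha 0.05, and 0.9 read as power.

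n = (10 × (1.960 + 1.282) / 7)² = 21.4, stated as 21; 21 × 1.3 = 27.3, stated as 28.

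The figure reproduces by the normal approximation and belongs to Visit 5 minus Visit 1. Under the planned paired t-test, n=21 gives 86% power for 7 points.

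**Step 6. Precision for Visit 5 minus Visit 3 (assumed SDs).** The documents give no SD for this contrast. SD 10 is carried over from 6.4, and SD 8 is an assumption. SD 12.7 is 9 × √2, for two uncorrelated measurements with the SD of 9 in 6.4. The half-width is t(0.975, 20) × SD / √21 with t = 2.086; for SD 10 that is 2.086 × 10 / 4.583 = 4.55. Power is from the noncentral t, two-sided 0.05, n=21.

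| Assumed SD | 95% CI half-width | Power, H = 3.5 | H = 5 | H = 7 |
|---|---|---|---|---|
| 8 | 3.64 | 48% | 78% | 97% |
| 10 | 4.55 | 33% | 59% | 86% |
| 12.7 | 5.78 | 23% | 40% | 67% |

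If all 28 complete, the half-width is 3.10 at SD 8 and 3.88 at SD 10.

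**Step 7. Attribution.** The same calculation applies to Visit 5 minus Visit 1 when H = 0. At n=21 and SD 10, an assumed albuterol shift of 2, 3.5, 5 or 7 points would make the primary test significant with probability 14%, 33%, 59% or 86%. The documents give no albuterol effect. Section 4.9, under which LABA/steroid combinations are not withheld on visit mornings, makes its size harder to guess.

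**The case against.** The strongest reply is that the 6.3 error is a template remnant. The synopsis states the null as baseline versus post-HS and says that this comparison is prioritised; 6.1, 6.4 and the opening of 6.3 agree. This stands: a reader might infer that the plan has albuterol as its primary test, or two rival primaries, and the documents taken together do not support that. What remains is that the primary hypothesis has to be inferred against its own display.

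A second reply is that HS is shorthand for the described regimen. Parts of the synopsis do say 7% HS with albuterol, pretreatment is disclosed, and the paired comparison of Visits 5 and 3 is already planned. That also stands in part. The combination is a legitimate estimand, and it would be wrong to infer that the primary contrast is invalid or that the study ignores albuterol. The shorthand still fails in 2.1, where the objective is the efficacy of HS.

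A third reply is that albuterol may be on board at the Visit 1 scan. Section 9 also says that asthmatic subjects are pretreated with albuterol before hypertonic saline, and sputum induction uses hypertonic saline. In that case the HS wording would be defensible. The visit narratives and the existence of a separate albuterol visit point the other way, but the text does not settle it, so rewording the estimand has to wait for that reconciliation.

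Finally, the probabilities in Steps 6 and 7 rest on assumed shifts and SDs. That is so, and they are illustrations only.

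**Conclusion.** The point holds in this form. Section 6.3 contradicts itself on the primary test, although the intended one can be recovered. On the described steps, Visit 5 minus Visit 1 estimates albuterol plus 7% HS and is worded as HS; this is conditional on an albuterol-free Visit 1 scan. The rank of Visit 5 minus Visit 3 is inconsistent. It should be fixed, but it does not undermine the design.

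On size: at n=21 the Visit 5 minus Visit 3 half-width is about 3.6 to 5.8 points over assumed SDs of 8 to 12.7. Power for an increment of 3.5 to 7 points runs from 48% to 97% (SD 8), 33% to 86% (SD 10) or 23% to 67% (SD 12.7).

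Two stronger readings are not supported. The Step 7 probabilities are not type I errors, because the stated null of no change from baseline is false whenever albuterol has an effect; they show only that significance cannot be credited to HS. Nor does Visit 5 minus Visit 3 isolate HS by itself: the visit order is fixed, the study is open label and there is no nebulised vehicle control, so period effects remain in both contrasts.

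**What to change.** 1. **First, reconcile the procedures.** Sections 3.1, 4.1, 5 (sputum induction), 9 and the section 14 schedule must agree on whether and when albuterol is given at Visit 1 relative to the scan. The MCC text in section 5 has HS inhaled at both Visits 3 and 5; it must be reconciled with 3.1, 4.3 and the schedule, which make Visit 3 albuterol only.
2. **Correct the hypotheses.** In 6.3, attach a zero mean for Visit 5 minus Visit 1 to the primary test and a zero mean for Visit 3 minus Visit 1 to the secondary test. Delete the 3% symbol and the sentence that calls baseline versus 7% HS secondary and exploratory. Rewrite the synopsis primary endpoint to match, and remove the 3% versus 7% comparison from 5.1.
3. **If the Visit 1 scan is confirmed albuterol-free,** word the primary objective and conclusion in the synopsis, 2.1, 5.1, 6.1, 6.3 and 6.4 as albuterol plus 7% HS versus baseline. Reword 2.2 as the added effect of 7% HS over albuterol alone, since HS is never given without albuterol.
4. **Give Visit 5 minus Visit 3 one rank,** secondary, in the synopsis, 6.2 and 6.3. Always report its estimate and 95% CI, and base any statement on the added effect of HS on it. State the limits from fixed order, open label and no vehicle control. Label any expected precision as an assumption and show the range of SDs.

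The cost is wording and ranking only, with no new scans, visits or participants. The downside is that the secondary contrast may be imprecise, and a null result there must be reported as inconclusive.

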Criteria for Inclusion and Exclusion:	
 1. Age 18-60. 2. Moderate to severe asthma at baseline (determined by Step 3 therapy or greater or by degree of impairment secondary to asthma). Subjects will be Well Controlled asthma at the time of enrollment, or Not Well Controlled as determined by National Heart, Lung and Blood Institute (NHLBI) Expert Panel Report 3 guidelines for diagnosis and treatment of asthma. Subjects who meet the Not Well Controlled criteria must be free of wheezing, and must be at their baseline prior to any hypertonic saline inhalation. 3. Subjects of childbearing potential must be non-pregnant, non-lactating, and using an acceptable method of birth control (an IUD with a failure rate of <1%, hormonal contraceptives, barrier method, or abstinence) for the duration of participation study; if practicing abstinence, the subject must agree to use one of the acceptable methods of contraception if she becomes sexually active.
	Exclusion Criteria
	
 1. Current tobacco smokers (or >10 pack years of smoking) or e-cigarette users (including use within 1 year of the study) 2. Other chronic illness, which could impact safety or study results 3. Radiation exposure within the past year that would cause them to exceed Federal radiation safety regulations.
Study Duration	
Each subject's participation will last up to 4.5 months.
 
The entire study is expected to last up to 6 years.

Study Phases	
Screening	(1) Baseline MCC : Informed consent obtained, medical history including radiation exposure, vital signs and lung function assessed with spirometry. FEV1 must be $\geq 70\%$ of predicted. A baseline MCC scan will be performed over 2 hours.
Study	
Treatment	(2) Baseline MCC with 4 puffs of albuterol : Subjects will return at least 1 week later for a MCC scan with 4 puffs of albuterol immediately after the start of the MCC measurement.
Follow-Up	(3) Acute effects of HS on MCC : At least 1 week after albuterol visit, subjects will receive 4 puffs of albuterol and a dose of 7% HS immediately after the start of MCC measurement over a 2 hour period to assess the acute effects of HS on MCC. Subjects will undergo sputum induction after each MCC visit.

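### Section 6.4 states 0.9 power at n=21, but the planned paired t-test gives 86% at SD 10; that SD is an unsupported assumption, and 28 recruits leave 21 pairs only if attrition is at most 25%

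*Combined protocol and SAP*

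**What the plan says.** Section 6.4 takes its variability from one earlier asthma study. That study, "in patients who would fit criteria for moderate asthma" and under baseline conditions, "found a mean average % retention of 21% with a standard deviation of 9" percent. The target is then set: "We wish to detect a difference of mean MCC equal to 7" percent, which Section 6.3 makes clear is in absolute percentage points. For the SD of the paired difference, Section 6.4 appeals to the pairing and says "we believe 10% to be a reasonable upper bound of the standard deviation of this difference in means". It concludes: "Assuming $\beta=0.9$ and $\alpha=0.05$, a sample size of $n=21$ would be adequate". The printed beta of 0.9 can only sensibly mean power.

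On losses, it says "We will inflate this by 30% to account for" attrition over several visits, which gives 28 recruits. No expected attrition rate is stated.

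The test named in Section 6.3 is "using a paired two-sided one-sample t-test with a 5% type I error rate". Neither document section gives a within-subject correlation, a test-retest SD or an SD for MCC after HS.

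**The concern.** Three statements in Section 6.4 carry the sample size: the power at 21 pairs, the description of SD 10 as an upper bound, and the allowance for attrition. A reader will take them together to mean that power is at least 90% under cautious assumptions. It is not clear that they say this. The calculation may not match the planned test. The bound depends on a correlation that is never given. Inflating by a percentage is also not the same as tolerating that percentage of losses.

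What is at stake is the chance of an inconclusive primary result. If power is lower than printed, that chance is higher than the 10% that the funder, the DSMB and readers would infer, and nothing in Section 6.4 lets them see by how much.

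**Working it through.** **Inputs.** Difference 7 points, SD of the difference 10, baseline SD 9, n=21, recruited 28 (all Section 6.4); two-sided alpha 0.05 and paired t-test (Section 6.3); power 0.90 (Section 6.4, printed as beta).

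**1. The plan's n.** By the normal approximation, n = (SD × (z₀.₉₇₅ + z₀.₉₀) / difference)² = (10 × 3.2415 / 7)² = 21.44. The printed 21 is this value rounded down; rounding up would give 22. Normal-approximation power at 21 is 89.4%.

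**2. Power under the planned test.** For the paired t-test, power comes from the non-central t distribution with n − 1 degrees of freedom and non-centrality (7/SD) × √n. At n=21 and SD 10 the non-centrality is 0.7 × √21 = 3.21.

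| Pairs | Power at SD 10 |
|---|---|
| 19 | 82% |
| 20 | 84% |
| 21 | 86% |
| 22 | 88% |
| 23 | 89% |
| 24 | 91% |

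The smallest n reaching 90% is 24.

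**3. Attrition.** 21 × 1.3 = 27.3, rounded up to 28, so the inflation is computed as described. The losses that still leave 21 pairs are 28 − 21 = 7, and 7/28 = 25%. Keeping 24 pairs would allow 28 − 24 = 4 losses, 4/28 = 14%. For comparison, 30% loss would leave 28 × 0.70 = 19.6, that is 19 or 20 pairs.

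**4. What SD 10 requires.** With baseline SD 9, post-HS SD s and within-subject correlation r, the variance of the difference is 81 + s² − 18rs. Setting this to at most 100 gives r ≥ (s² − 19)/(18s).

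| Assumed post-HS SD | Correlation needed for SD of difference ≤ 10 |
|---|---|
| 6 | 0.16 |
| 7 | 0.24 |
| 8 | 0.31 |
| 9 | 0.38 |
| 10 | 0.45 |
| 12 | 0.58 |

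The post-HS SDs are assumptions, since the documents give none. Below about 4.4 (√19) any non-negative correlation is enough.

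**5. Power with 21 pairs over a range of SDs (paired t-test, 7 points).**

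| SD of difference | Example that produces it | Power |
|---|---|---|
| 9.0 | both SDs 9, r = 0.5 | 92% |
| 10.0 | both SDs 9, r = 0.383 | 86% |
| 10.82 | SDs 9 and 12, r = 0.5: √(81 + 144 − 108) | 80.5% |
| 12.73 | both SDs 9, r = 0: √162 | 67% |

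**The case against.** The best defence is that Section 6.4 is hedged. It offers a belief about a reasonable bound, not a mathematical maximum, and repeat scans in one person are unlikely to be unrelated. This stands. The r = 0 row is an extreme, and a correlation above 0.38 is quite possible. The post-HS SD could also be below 9: if SD scaled with the mean as retention fell from 21 to 14, it would be 9 × 14/21 = 6, and a correlation of 0.16 would be enough.

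Four stronger readings are therefore tempting but not supported:

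- *That the baseline SD of 9 contradicts SD 10.* It does not. The contradiction would need a correlation or a post-HS SD that the documents do not give.
- *That a mixed population makes 10 too small.* The synopsis does admit a wider group than the source study ("Subjects will be Well Controlled asthma at the time of enrollment, or Not Well Controlled"), and severe as well as moderate asthma. But that widens the spread between subjects, which largely cancels in a paired difference. It is no evidence of greater within-subject variability.
- *That the plan assumed 30% attrition and miscalculated.* It says only that n is inflated by 30%, and 28 is the correct result.
- *That a non-significant result will be read as evidence of no effect.* Section 6.3 says a p-value above 0.05 will be treated as inconclusive, and it tabulates 95% confidence intervals.

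None of this answers the t-test result. Even granting SD 10 in full and no loss below 21 pairs, the planned test does not reach the stated 0.9.

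**Conclusion.** The point holds as a misstatement of power and an unsupported label, not as a proven shortfall in the design. At the plan's own SD and n, power is 86% rather than 90%, so the chance of missing a true 7-point difference is about 14% instead of 10%. If losses leave 19 or 20 pairs, power is 82% or 84%. SD 10 should be read as an assumption. Over the SDs shown, power with 21 pairs runs from 92% down to 67%, and the documents do not say where in that range the trial lies.

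This rests on reading beta as power, the 7% as absolute points, and normally distributed differences as Section 6.3 assumes. For an open-label proof-of-concept study the gap at SD 10 is modest, and it does not invalidate the trial or the planned analysis.

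**What to change.** Amend the wording of Section 6.4:

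1. Replace the statement of 0.9 power with about 86% power for 21 pairs at SD 10 under the two-sided paired t-test, and label the quantity as power, not beta.
2. State that 28 recruits leave 21 pairs with up to 25% attrition (7 losses), and give power for 19, 20 and 21 pairs: 82%, 84% and 86%.
3. Replace the upper-bound wording with an assumed SD, and show power for 21 pairs on both sides of it: 92% at SD 9, 86% at 10, 80.5% at 10.82 and 67% at 12.73. If the investigators hold test-retest MCC data, cite the SD of the difference from them.

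The cost is a protocol wording change and a less favourable printed power. It needs no extra patients and no change to visits or analysis.

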6.5 Interim Analysis

Interim analyses of efficacy of 7% HS will be performed.

7. STUDY INTERVENTION (drug, device or other intervention details)

- **Description:** Sodium chloride 7% solution, which is commercially available as Hypersal® (PARI Respiratory Equipment, Inc, Midlothian, VA).
- **Receipt/Storage:** HS will be delivered and stored within the CEMALB.
- **Packaging/Labeling:** This is an open label study.
- **Dosing:** 4mL vial of HS is nebulized and inhaled until the dose is complete, typically 15 minutes.
- **Treatment compliance and Adherence:** Subjects are observed during all dosing periods.
- **Drug Return/Destruction:** NA
- **Drug Accountability:** NA

8. STUDY INTERVENTION ADMINISTRATION (if applicable)

- **Randomization procedures:** N/A
- **Blinding procedures:** This is an open label study.

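### Section 6.4 calls 21 pairs adequate for 90% power, but at its own SD of 10 the planned paired t-test has 86% power with 21 pairs and needs 24

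*Combined protocol and SAP*

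**What the plan says.** All the sample size inputs are in section 6.4 of the combined protocol and SAP. The target is given as "We wish to detect a difference of mean MCC equal to 7" percent, and section 6.3 makes clear that "this difference has a unit of absolute percentage points". On variability, section 6.4 says "we believe 10% to be a reasonable upper bound of the standard deviation of this difference in means". It then concludes: "Assuming $\beta=0.9$ and $\alpha=0.05$, a sample size of $n=21$ would be adequate". For attrition it adds "We will inflate this by 30% to account for" "attrition with multiple study visits, taking the recruited sample to n=28". Section 3.3 repeats the total of 28.

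Section 6.3 fixes the test: the null hypothesis is tested "using a paired two-sided one-sample t-test with a 5% type I error rate". Section 6.4 names no formula or software for its calculation.

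**The concern.** The number of pairs in a sample size statement should deliver the stated power for the test that will be run, at the SD chosen for sizing. A standardised effect of 7/10 = 0.70 with about 20 pairs is a setting where the t distribution matters: a normal formula understates the requirement by two or three pairs. The figure 21 is lower than even the normal formula gives when rounded up.

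The label is also wrong. Beta conventionally denotes the type II error, so a beta of 0.9 would mean 10% power. The intended meaning is clearly 90% power.

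This paragraph is the only justification for enrolling 28. If 21 is too low, part of the allowance described as cover for attrition is in fact needed to reach the stated power, and the study team does not know how many evaluable pairs it must protect.

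**Working it through.** **Inputs.** Difference δ = 7 points, SD of paired differences σ = 10 (upper bound), α = 0.05, and power 0.90 as the reading of the stated beta (all from section 6.4). Two-sided paired t-test (section 6.3). Standardised effect d = 7/10 = 0.70. The full 5% is assumed available at the final test.

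**Reproducing the plan's figure.** The normal approximation for paired data is

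n = (z₀.₉₇₅ + z₀.₉₀)² × σ²/δ² = (1.960 + 1.282)² × 100/49 = 21.44.

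Rounded up this is 22; rounded down it is 21. At n = 21 the same approximation gives power Φ(0.70 × √21 − 1.960) = 89.4%. So 21 is close to the normal result but rounded the wrong way. Other routes do not give 21: for 90% power a one-sided normal formula gives 18 and a one-sided t-test 19.

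**The planned test.** Under the alternative, the paired t statistic has a noncentral t distribution with n − 1 degrees of freedom and noncentrality 0.70 × √n. Power is the probability that it falls beyond the two-sided 5% critical value. For example, at n = 21 the noncentrality is 3.208 and the critical value 2.086; at n = 24 they are 3.429 and 2.069.

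| Pairs | Power at SD 10 |
|---|---|
| 20 | 84.4% |
| 21 | 86.2% |
| 22 | 87.9% |
| 23 | 89.4% |
| 24 | 90.7% |
| 28 | 94.6% |

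The smallest n with at least 90% power is 24. A simulation of 400,000 runs at each size agrees: 86.3% at 21 and 90.8% at 24. With 21 pairs the difference detectable with 90% power is 7.4 points; with 24 it is 6.9.

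**Sensitivity to the SD**, keeping δ = 7:

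| SD of differences | Power with 21 pairs | Pairs needed for 90% |
|---|---|---|
| 9 | 92.3% | 20 |
| 9.4 | 90.1% | 21 |
| 9.5 | 89.5% | 22 |
| 10 | 86.2% | 24 |

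The SD at which 21 pairs give exactly 90% is 9.41.

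**Attrition.** The plan's inflation is 21 × 1.3 = 27.3, rounded up to 28, which adds 7 to 21. Counted from 24, the margin is 28 − 24 = 4 (4/28 = 14%). At SD 10, starting from 28 enrolled:

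| Losses | Evaluable pairs | Power |
|---|---|---|
| 0 | 28 | 94.6% |
| 4 (14%) | 24 | 90.7% |
| 5 (18%) | 23 | 89.4% |
| 7 (25%) | 21 | 86.2% |

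If 30% of those enrolled were lost, 28 × 0.7 = 19.6, so 19 or 20 pairs would remain, with 82% to 84% power.

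**The literal label.** With beta = 0.9 (10% power), 3 pairs would be enough (11.6%), so this cannot be what was meant.

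**The case against.** The strongest reply is that the gap is small and arises only at an SD chosen to be pessimistic. It is 3.8 points of power, and at an SD of 9 the 21 pairs give 92.3%. Also, 28 subjects are enrolled, not 21; with all 28 evaluable, power is 94.6%. The study is an open-label proof of concept, and section 6.3 treats a p-value above 0.05 as inconclusive, which limits the harm from somewhat lower power.

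Much of this stands and sets the weight of the point. It does not remove the error. The plan chose to size the trial at SD 10, so its stated n should give the stated power there. Nor do the documents show that the true SD is comfortably lower. Section 6.4 cites a between-subject SD of 9 at baseline and gives no within-subject correlation ρ. If the SD is 9 at both visits (an assumption), the variance of the difference is 2 × 81 × (1 − ρ). An SD of 10 then corresponds to ρ = 1 − 100/162 = 0.38, and 9.41 requires ρ of at least 1 − 88.5/162 = 0.45. Neither value can be ruled out from the documents. As for the 28, the extra 7 are set aside for attrition, so they cannot also make up the shortfall.

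It is also fair to say that the origin of 21 is an inference, since the plan names no method. The conclusion does not depend on it.

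**Conclusion.** The concern holds. For the test in section 6.3 and the inputs in section 6.4, the requirement is understated by 3 pairs (24, not 21). With 21 pairs at SD 10, the type II error is 13.8% instead of 10%. At that SD, 28 enrolled keeps 90% power with up to 4 losses, not the 7 that the inflation was meant to cover.

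This rests on reading the stated beta as power, on approximately normal differences, and on the full 5% being used at the final test. It is a moderate planning error confined to SDs above about 9.4. The type I error, the analysis and the estimate are unaffected.

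A related matter is kept separate here: section 6.5 says "Interim analyses of efficacy of 7% HS will be performed" and gives no alpha spending. None of the figures above depends on it, but any alpha spent before the final test would lower final power further.

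**What to change.** Restate section 6.4 along these lines: at the upper-bound SD of differences of 10 points, a two-sided 5% paired t-test to detect 7 points has 90% power (beta = 0.10) with 24 evaluable pairs and 86% with 21. Enrolling 28 keeps at least 90% power with up to 4 losses (14%); 7 losses (25%) give 86%, so the full attrition allowance is not covered at 90% power at this SD. With an SD of 9.4 or less, 21 pairs give at least 90%.

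Name the method used (noncentral t). If alpha is to be spent at the interim analyses of section 6.5, recompute these figures at the final alpha.

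The cost is one paragraph of wording, with no additional subjects and no change to the analysis. The stated power becomes slightly less favourable, and the team gains a working target of at least 24 evaluable pairs.
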